Cerebellar 5-HTT V_T (V_2) was higher in healthy volunteers than depressed bipolar subjects $(21.49 \pm 5.11 \text{ mL/g vs. } 17.04 \pm 2.58$ mL/g, Students' t = 4.43, df = 56, p < .001), and therefore cannot explain our results. Such an effect leads to an underestimate of the 5-HTT BP₁ in the regions of interest, with the effect being more pronounced in the healthy volunteers. Thus, observed differences in BP₁ between healthy and depressed bipolar subjects are likely an underestimation of the actual physiological difference. Because of the difference in cerebellar V_T, outcome measures that are more sensitive to this measure (BP₂ = BP₁/V_T) show no difference between bipolar subjects and controls. A major limitation of studies that do not utilize arterial sampling is that BP₂ is the *only* outcome measure that can be obtained.

Whether lower 5-HTT BP₁ observed in depressed bipolar subjects is due to primary deficits in the serotonin system or secondary to other neurochemical abnormalities and whether this abnormality is a trait or only present during the depressed state requires further inquiry. Studies examining 5-HTT binding during periods of mania or euthymia or measuring 5-HTT

binding concomitantly with GABA or glutamate levels in brain may elucidate these issues. Nonetheless, these findings, the first in vivo evidence of a brain abnormality of this magnitude in bipolar disorder, suggest that bipolar depression is associated with more extensive serotonergic dysfunction than unipolar depression and may be a more severe manifestation of illness along a spectrum of mood disorders.

C.2. 5-HT_{1A} in Bipolar Disorder.

Stony Brook University Human Subjects Committee (IRB) PSF 2/23/15 Page 6 of 37

IRB# 2012-1826-F PI: [name]

Carson 2004	Laruelle 1994 ²³	Carson 1997 ²⁴	Relationship to receptor parameters	Equilibrium calculation	Kinetic calculation	Graphical calculation
BP BP ₁ BP ₂	V ₃ V' ₃ V'' ₃	S' S R	$\begin{aligned} B_{\text{max}}/K_D \\ f_1 B_{\text{max}}/K_D \\ f_2 B_{\text{max}}/K_D \end{aligned}$	$C_3/C_1f_1 \ C_3/C_1 \ C_3/C_2$	$K_1k_3/k_2k_4f_1\\K_1k_3/k_2k_4\\k_3/k_4$	$(V_T - V_{REF})/f_1$ $V_T - V_{REF}$ $(V_T/V_{REF}) - 1$

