Statistical analyses performed included Student's t-test, one way analysis of variance, and linear mixed models analysis with subject as the random effect. Model fitting was computed using both SPSS 11 for Mac OSX (www.spss.com) and R (www.R-project.org). When multiple regions were considered in a single

[figure not shown]

Figure 4: Trends for higher 5-HT_{1A} BP in male bipolar patients and lower 5-HT_{1A} BP in female bipolar patients.

analysis, region was included as a fixed effect, and the analysis was performed on the natural log of BP, in order to account for heterogeneity of variances across regions. Significance was defined as p < 0.05 and p-values are reported without multiple comparison adjustment. tests were two-sided. In all models, there were no interactions, first or higher order, therefore, the interaction terms were not included in the models. Data are presented as mean \pm standard deviation.

There was no difference in percentage of females between controls (56%) and bipolar subjects (60). They also did not differ in age (controls = 37.3 ± 14.5 , BPD = 39.04 ± 10.0 , p = 0.640). The control population presented here is the same as in our previous publication.²²

Across all regions there was slightly higher BP in BPD subjects scanned during a MDE compared to controls but this did not reach statistical significance (F = 0.592; df = 1, 54; p = 0.444; Figure 3). We have previously reported that females have significantly higher 5-HT_{1A} BP than men and that there is a correlation between lifetime aggression scores and BP. 153 As this is preliminary data, we do not have lifetime aggression scores for all the subjects but when we include gender in the linear mixed effects model we get a significant gender by diagnosis interaction (F = 5.99; df = 1, 54; p = 0.018). In contrast to the our findings in unipolar depression, it appears that male bipolar subjects

Stony Brook University Human Subjects Committee (IRB) PSF 2/23/15

Page 8 of 37

IRB# 2012-1826-F PI: [name]

have higher 5-HT_{1A} BP compared to male controls while female bipolar patients have lower BP compared to female controls (Figure 4). We have also shown that prior medication status has a major effect on 5-HT_{1A} BP²² however 90% of the bipolar subjects had been previously exposed to medication.

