We will use the radiotracer [11C]DASB to measure serotonin (5-HT) transporter binding and [11C]CUMI-101 to measure serotonin receptors in the brain of depressed or recently depressed bipolar subjects using Positron Emission Tomography (PET) before and after treatment with a mood stabilizer. We propose to assess how the clinical responses to two types of mood stabilizer treatment relate to the state of the serotonin system. The two treatments we intend to compare are lithium and lamotrigine. We propose to perform [11C]CUMI-101 and [11C]DASB in 38 medication free bipolar subjects during a major depressive episode and compare 5-HTT and 5-HT_{1A} binding potential in 38 healthy volunteers. We will also examine the diagnostic specificity of lithium response by studying 10 unipolar depressed subjects in an identical manner.

We will obtain blood samples from all subjects in the protocol in order to be able to evaluate their genetic information. We plan to analyze the DNA from the blood to assess for genome wide and single nucleotide polymorphisms and their associations with MRI and PET brain imaging measures. For example, the effects of the C(-1019)G 5-HT1A promoter polymorphism has been shown to affect the binding of our 5-HT1A tracers in humans. The genetic information may also be used to study the general pathophysiology of major depression, bipolar disorder or past suicidal ideation in the subjects. Blood RNA will also be evaluated because it tells us whether the gene variants are associated with altered gene expression. We expect gene variants with altered expression levels to be of greater pathophysiological consequence.

2. Research Site

Stony Brook University Human Subjects Committee (IRB) PSF 2/23/15

Page 9 of 37

IRB# 2012-1826-F PI: [name]

MRI scans, research interviews, clinical assessments and treatment will take place at Stony Brook University Medical Center. PET scans will take place at the Yale University PET Center in New Haven, CT.

3. Study Sample

86 subjects in total are proposed. The power calculations are below.

Age range: 18-70

Total subjects: N = 86 (38 bipolar, 38 healthy volunteer, 10 unipolar)

Gender: Male and female representation are about equal.

No ethnic/racial/gender group is excluded.

4. Screening

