PSF 2/23/15 Page 18 of 37

The order of [\(^{11}\)C]CUMI-101 and [\(^{11}\)C]DASB administration may be reversed, or subjects may participate in only one scan (either [\(^{11}\)C]CUMI-101 or [\(^{11}\)C]DASB),.

In cases where the subject has a hemoglobin level less than 12 for males and less than 11 for females, we would forgo blood drawing for the [11C]DASB scan except for one sample to be taken at the 50 minute time point, as outlined in the simultaneous estimation (SIME) approach. Likewise, we would forego blood drawing for the [11C]CUMI-101 scan except for one sample at the 60 minute time point. We have recently confirmed that this provides an excellent estimate of the plasma parameters necessary for quantification and modeling of this radioligand. It involves drawing one 12 cc sample off the arterial line at the 50 min post-radioligand injection time point. Therefore, instead of 120 cc being drawn during the DASB scan, we would reduce the blood drawn to 12 cc.

In the case that the two injections are planned but cannot be done on the same day once the PET procedures have been started, subjects may be asked to return on a separate day in order to complete the scans. If the PET procedure has to be rescheduled and placement of another aline is required, subject consent will be sought.

After the acute treatment period, the patients who are on either lithium or lamotrigine will have a second PET scanning session that is identical to the first: up to 20 mCi or less of [11C]CUMI-101 and up to 20 mCi of [11C]DASB. Healthy volunteers will not have follow up scans.

Alternate Location and Tracer for PET Scans

Due to limited availability of PET scans at the Yale PET center, alternative arrangements will be made for subjects at Stony Brook Medicine. In cases where the subject cannot accommodate a trip to the Yale PET center or the Yale PET center cannot accommodate for enough scans due to decreased scan staff, PET/MRI scans may take place at the Siemens Biograph mMR-System located at the Ambulatory Imaging Center using [18F]MeFWAY. Similar to the [11C]CUMI-101 scans being performed at the Yale PET center, [18F]MeFWAY also has the capability to examine 5-HT_{1A} binding. Only bipolar and unipolar patients will be scanned at Stony Brook, when Yale is unable to accommodate the number of scans necessary. Healthy controls will continue to be scanned at Yale PET Center.

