To assess the impact of lithium on the neuroreceptor measures we conservatively use the higher test/retest variability of the [¹¹C]DASB compound and assume a 20-25% change in both 5-HT_{1A} and 5-HTT after chronic lithium based on preclinical data. ¹4,16-18 Assuming 50% of the subjects complete the lithium treatment and repeat scans and this degree of change, we have a power of between 79% and 90% as this is a paired analysis. Estimated outcome measures will be analyzed for all ROIs and all patients in a linear mixed model with patient as random effect and ROI and remission status as fixed effects. Our previous studies have demonstrated that the standard deviation of BP across patients increases approximately linearly with the mean of the region, and so the BP values are first log-transformed in order to satisfy the assumptions of the modeling (constant variance across regions). For the pre/post imaging of the non-remitters, a linear mixed model will again be used with ROI and condition (before/after) as fixed effects and with two levels of random effects -- a patient effect and a study within patient effect. Many potential covariates will also be measured for each patient and will be included in the model when appropriate. Modeling will be done using R software (www.r-project.org).

F. Funding Status, Details

The study is currently funded through the National Institutes of Health (NIH) through May 31, 2017. Grant Title: Lithium's Molecular Mechanism of Action and the Pathology of Bipolar Disorder

G. Human Subjects Research Protection from Risk

1. Risk to Subjects and 2. Adequacy of Protection Against Risks

Risks associated with participation in this study are related to 1) Drug-free interval; 2) placement of intraarterial catheter; 3) blood sampling; 4) discomfort during scanning (PET and MRI); 5) MRI scan; 6) radiation exposure; 7) toxicology (idiosyncratic reaction to the tracer); 8) genetic testing/confidentiality; 9) pregnancy and 10) risks associated with lithium/lamotrigine use.

Stony Brook University Human Subjects Committee (IRB) PSF 2/23/15

Page 23 of 37

IRB# 2012-1826-F PI: [name] 1. Drug-free interval

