Bipolar disorder is a major health problem in which the serotonin system may play a role in pathogenesis and/or treatment. An urgent need exists for a reliable biochemical test for bipolar disorder. Therefore, study of the serotonergic system should be conducted in the untreated depressed state where these measures may have potential as diagnostic tools as well as providing important information about the pathogenesis of bipolar disorder and biochemical heterogeneity of depressive disorders. Repeating these tests after treatment will assist in determining the mechanism of action of mood stabilizers, the potential of this type of PET scan as a biochemical monitor of clinical response as well as help to determine whether alterations in function are state or trait-dependent. Such studies can also improve knowledge regarding the mechanism of action of mood stabilizers, and may lead to the design of better medications.

H. Data Safety Monitoring Plan (for more than minimal risk studies)

Access to research data will be allowed only to members of the research team or institutional personnel as part of a routine audit. Records may be reviewed by state or federal regulatory agencies and their personnel. Research records, like other medical and clinical records, will be kept confidential to the extent permitted by law. There are legal advocacy organizations that have the authority under state law to access otherwise confidential subject records, though they cannot disclose this information without the subject's consent. All hard copies of records are kept in locked files. Coded computer files will be stored in a database which is password protected and behind an institute and department firewall.

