Official Title: PET and MRI Brain Imaging of Bipolar Disorder

NCT: NCT01880957

Document Date: 11/14/2017

Proposed Statistical Plan for [11C]-DASB (5-HTT) & [11C]-CUMI-101 (5-HT1A) from [name] **Bipolar Study**

Outcomes

DASB: V_T/f_p + bootstrap ROI error

CUMI: BP_F + bootstrap ROI error (BP_{ND}??)

A priori ROIs

DASB: acn, amy, midbrain, gcirc

CUMI: acn, amy, cin, dlPFC, parahippocampal gyrus, hippocampus, raphe

Statistical methods:

Linear mixed models with subject fit as random variable LMM also with DASB & CUMI reference regions and fp

Key outcomes: p-values for main effects/interactions; overall model R² & p-value; standardized & unstandardized β's, 95% CIs, p-values for post-hocs

Covariates

DASB: age

CUMI: age, sex, previous med status (dichotomous – w/n 4 years)

Post-Treatment

Sample: HC, pre BPD, post BPD

Question 1: Do post-treatment BPD levels of DASB or CUMI differ from pre-treatment levels and HCs?

Interactions of interest:

Group (relationship btw brain & Group across all regions) **Group*ROI** (ROI-specific relationship btw brain & Group)

Treatment Effects

Sample: pre/post BPD pairs

Tx response: % change in HDRS-24 (continuous) and remitter/non-remitter (dichotomous)

Question 2: Is the % change in DASB or CUMI associated with the treatment outcome?

Interactions of interest:

AHDRS (relationship btw brain & Tx outcome across all regions) **ΔHDRS*ROI** (ROI-specific relationship btw brain & Tx outcome)

Dichotomous

Interactions of interest:

Remission (relationship btw brain & Tx outcome across all regions)

Predicting Treatment Outcome

Sample: pre BPD with pre HDRS-24 + >7-week HDRS-24

Tx response: % change in HDRS-24 (continuous) and remitter/non-remitter (dichotomous) (responder ??)

Question 3: Do pre DASB or CUMI in any of the *a prioris* predict treatment response? Are the *a prioris* independent predictors of treatment response?

Interactions of interest:

PET roi (pre-treatment PET in ROI predicts treatment response)

Interactions of interest:

PET_roi (any significant ROIs are independent predictors of Tx response (over and above the other ROIs))

Same models fit with dichotomous remission status

Additional question: Do pre DASB & CUMI together predict more of the variance in treatment response than either method alone?

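### The before/after PET change is attributed to lithium, but the planned contrast cannot separate lithium from time, longer time off earlier drugs or recovery, and the SAP pools lithium with lamotrigine

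*Protocol*

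**What the plan says.** **Claim.** Protocol section A, Aims 2 and 3, sets out to assess the effect of lithium on 5-HTT and 5-HT1A binding, expecting a rise in the first and a fall in the second. Section G.4 says: "Repeating these tests after treatment will assist in determining the mechanism of action of mood stabilizers". The same section also expects the repeat scans to show whether alterations depend on state or trait.

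**Who is rescanned.** Section D.5, PET Studies: "the patients who are on either lithium or lamotrigine will have a second PET scanning session that is identical to the first". For controls: "Healthy volunteers will not have follow up scans". Controls may have an optional second MRI at about 12 weeks, but not a second PET scan. Aim 5 adds repeat DASB scans in 10 unipolar patients, who receive only lithium. Section D.1 states: "The two treatments we intend to compare are lithium and lamotrigine".

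**How drug is assigned.** Under Treatment Choice, lamotrigine goes to patients with earlier lithium failure or refusal, those who cannot tolerate lithium, and those with less than 50% HDRS improvement at 6 weeks. Nothing is randomised.

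**Models.** Section E specifies a mixed model with "ROI and condition (before/after) as fixed effects", written for the non-remitters; another model there includes remission status. SAP Question 1 uses "Sample: HC, pre BPD, post BPD", with Group and Group-by-ROI terms and no term for drug. SAP Question 2 relates percentage change in binding to percentage change in HDRS-24 and to remission. Covariates are age for DASB, and age, sex and a yes/no previous-medication status for CUMI.

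**The concern.** A before/after contrast in treated patients measures everything that differs between the two scans. The protocol itself supplies reasons why binding might differ for causes other than lithium.

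- **Earlier medication.** Section C.2 reports that "prior medication status has a major effect on" 5-HT1A binding. The minimum washout before PET is 21 days. A lithium patient rescanned on schedule is scanned at least 6 weeks after reaching the therapeutic or highest tolerable dose. Someone at the washout minimum at baseline is thus at least 21 + 42 = 63 days off earlier drugs at rescan, plus titration time.
- **Clinical state.** Section C.1 says of the low 5-HTT binding that "whether this abnormality is a trait or only present during the depressed state requires further inquiry".
- **Selection.** The 6-week switch rule moves patients with little improvement off lithium, so those still on lithium at rescan may be mainly the recovered ones.

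At stake is the main conclusion of Aims 2 and 3. A significant change would be read as lithium's molecular action when the data show only that binding changed while patients took lithium. Pooling adds a second problem: a post-treatment bipolar group containing lamotrigine patients does not estimate the lithium change, and it leaves the intended comparison of the two drugs without a model term.

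**Working it through.** **1. What the contrast estimates.** For a lithium patient write change = L + T + W + M, where L is lithium, T time or repeat scanning, W longer time off earlier drugs, and M change in clinical state. The first scan is off lithium and the second on it in every such patient, so the condition column and the drug column are identical. The condition coefficient estimates only the sum. The plan does have a time term; it is fully aliased with treatment. Controls, with one scan each, inform the level but not the change.

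**2. What the covariates do.** Previous-medication status x is constant within a patient. As a main effect it contributes γx before and γx after, so its contribution to the change is γx − γx = 0. It would need an interaction with condition, and for DASB it is not listed at all.

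**3. What the other rescanned groups do.**
- *Lamotrigine.* With G for its own effect, lithium change minus lamotrigine change is (L − G) plus any group difference in T, W and M. G is not known to be zero: Aim 4 says lamotrigine alters 5-HT1A. The groups differ by design in lithium history and response.
- *Unipolar.* All receive lithium, so the contrast with bipolar patients compares diagnoses; it does not isolate L.

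**4. The stated power.** Inputs from section E: 50% of 38 = 19 pairs, a 20–25% change, log-transformed binding, power 79–90%. The SD of change, alpha and sidedness are not given there; I assume two-sided 0.05, as in section C.2, and solve backwards for the SD.

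Paired t-test: d = log(1 + change)/SD, noncentrality = d√19, 18 df, SD = 0.276.

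| Change | log | d | d√19 | Power |
|---|---|---|---|---|
| 20% | 0.182 | 0.661 | 2.88 | 78% |
| 25% | 0.223 | 0.809 | 3.52 | 92% |

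SDs of 0.274–0.278 bring both ends within 2 points of the stated range. On the raw percentage scale, an SD fitted to 79% at the low end gives 93% at the high end, a poorer fit. The stated range is plausible but cannot be derived forward. Nothing in the calculation refers to a comparator, so it is power for any change.

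**5. If lithium does nothing.** Same test with L = 0 and an upward non-drug change:

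| Non-drug change | log | d√19 | Significant (SD 0.276) | SD 0.272 to 0.284 |
|---|---|---|---|---|
| 0% | 0 | 0 | 5% | 5% |
| 5% | 0.049 | 0.77 | 11% | 12% to 11% |
| 10% | 0.095 | 1.51 | 30% | 30% to 28% |
| 15% | 0.140 | 2.21 | 55% | 56% to 53% |

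The 5–15% values are mine; the documents give no untreated change.

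**6. Precision of a between-drug comparison.** If 19 lithium patients were set against 19 others with the same SD (an assumption), noncentrality = d√(19/2) gives 2.04 and 2.49, or power of 51% and 68% for a 20% and 25% difference in change. With 10 comparators it is 37% and 51%.

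**The case against.** A good deal can be said for the plan.

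- A reader might infer that nobody else is rescanned. That is wrong: lamotrigine and unipolar patients are, and the lithium–lamotrigine comparison is a stated intention. What is missing is an untreated or randomised rescanned group and a drug term. Patients who tolerate neither drug are also rescanned as non-responders, but the protocol does not say what they are then taking or plan them as a comparator.
- A reader might infer that mood is ignored. It is not. The section E before/after model is written for non-remitters, which excludes full recovery though not partial improvement. SAP Question 2 relates binding change to HDRS change. An association there does not show which drives the other, and SAP Question 1 carries no such restriction.
- Section C.1 reports that the 5-HTT deficit was independent of depression severity, and section C.2 found no significant overall 5-HT1A group difference (p = 0.444). These points stand against assuming that patients recover part of a 16–27% deficit. The severity finding is cross-sectional, however; section C.1 still leaves the state-or-trait question open, and the earlier-medication route is untouched.
- Section G.4 is hedged, and an uncontrolled design is a known limit of mechanistic imaging. True, but the aims are worded as effects of lithium and neither document limits the claim.

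It is also tempting to use the CUMI test/retest CV of under 10% and obtain much higher false-positive rates. A CV of 10% implies an SD of change of about 14% (10% × √2) and essentially 100% power at a 20% change, which does not match the stated 79–90%. I do not use it.

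**Conclusion.** The concern holds as a limit on what may be concluded. The before/after term and the pre- versus post-treatment bipolar contrast are fully aliased with time, longer time off earlier drugs and recovery, and no rescanned group isolates lithium. The SAP also leaves out the drug factor that the protocol's stated comparison requires. This follows from the design and needs no numerical assumption.

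The size is illustrative: about 11%, 30% or 55% significant results with no lithium effect, for a non-drug change of 5%, 10% or 15%. It rests on 19 pairs, two-sided 0.05, a back-solved log-scale SD of about 0.276, a simple paired test in place of the mixed model, and assumed drifts. It should not be read as an estimate of this trial's error rate. Nor do the documents show that lithium has no effect or that drift of this size occurs; they show only that the plan could not tell the difference. The plan should be changed on this point, but the scans remain informative.

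**What to change.** 1. **Wording.** In Aims 2–3 and SAP Question 1, report the contrast as *change during lithium treatment*. Do not attribute it to lithium's mechanism on that contrast alone, and carry the same limit into section G.4. In section E, describe the 79–90% as power to detect any before/after change.
2. **Model.** In SAP Question 1, add drug at rescan (lithium or lamotrigine) and its interaction with condition among bipolar patients, with the ROI terms kept. Report the lithium change separately, and the difference from lamotrigine as a non-randomised comparison. State how patients who switched, or who tolerated neither drug, are classified.
3. **Supportive analyses.** Add days since last earlier psychotropic, interacting with condition, for both tracers. In lithium patients, relate PET change to the lithium level already measured at the repeat scan.
4. **A rule to avoid.** Do not declare a lithium effect because change persists at zero HDRS change. Drift from clearing earlier drugs would pass that test. Few lithium patients are likely to have zero change after the 6-week switch rule. If binding change leads to recovery, conditioning on HDRS change would also remove part of a real effect.

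**Cost.** Protocol and SAP text, one added factor with its interaction, and a variable obtainable from the medication history; no new scans or patients. The price is a weaker claim and wide intervals at about 19 pairs. The 0.8–1.2 mEq/l target leaves a narrow range for the lithium-level analysis.

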 (8) Current, past or anticipated exposure to radiation, that may include: being badged for radiation exposure in the workplace participation in nuclear medicine procedures, including research protocols in the last year.* (9) A neurological disease or loss of consciousness for 	1. Subjects will undergo a clinical interview, during which they will be asked whether or not they have worked with radioactive substances or have been badged in the past. In addition, they are asked about any prior chemotherapy or radiation treatment. 2. A research assistant will check our database to ensure that the subject has not participated in an imaging study within our department in the past year. Clinical interview
more than a few minutes (10) Medicinal patch that cannot be removed**	Medical history (by a physician),
(11)Patients who are responding satisfactorily to psychiatric medications, because they will not be washed-out for purposes of this study	physical exam. History
(12) A documented history of a lack of response to a trial of adequate dose and duration of both lithium and lamotrigine defined as minimal clinical response to lamotrigine 200 mgs for at least 4 weeks or lithium serum levels of at least 0.8 (or dose >= 900 mgs) for at least 4 weeks	History
(13) Patient is unlikely to be able to tolerate medication washout	Clinical interview
(14) Claustrophobia	Clinical interview

Approved: 12/13/2019
Expiration Date: 12/12/2020
Stony Brook University Human Subjects Committee (IRB)
PSF 2/23/15

Page 12 of 37

IRB# 2012-1826-F PI: [name]

(15) Blood donation within 8 weeks of the start of the study.	Clinical interview
(16) History of a bleeding disorder or are currently taking anticoagulants (such as Coumadin, Heparin, Pradaxa, Xarelto).	History

^{*} Subjects will be eligible if the injected dose and dosimetry of the radiotracer are known and the cumulative annual exposure of the previous study and this study is lower than the annual limit for research subjects defined by the FDA (see below)

HEALTHY VOLUNTEERS:

INCLUSION:		
(1) No lifetime history of Axis I disorders other than	Structured Clinical Interviews I	
specific phobia, social phobia, and/or adjustment	for DSM IV; clinical history and	
disorder.	interview	
(2) Age range 18-70 years.	Interview	
(3) Willing to travel to Yale University for PET	Interview	
scanning.		
EXCLUSION:		
(1) Past or present alcohol/substance abuse or	SCID; Urine drug screen	
dependence except for cannabis use disorders,		

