After 6-10 weeks from the time of therapeutic or highest tolerable dose of treatment with either agent they will have repeat [\frac{11}{C}]CUMI-101 and [\frac{11}{C}]DASB PET scans. Blood levels of the lithium will be measured at the time of the repeat scan. At 6 weeks, if patients have not shown at least a 50% improvement in their HDRS score from the baseline interview they will be switched to lamotrigine. Similarly, if patients cannot tolerate treatment, they will be switched to lamotrigine and we will repeat both [\frac{11}{C}]CUMI-101 and [\frac{11}{C}]DASB scans 4-10 weeks after subjects are on therapeutic levels of lamotrigine. If subjects cannot tolerate either treatment, or if the subject scores a CGI-I (severity of illness) score of 4 ("moderately ill") or more after the week 4 visit for two visits in a row, and/or a CGI-II (global improvement) score of 6 ("much worse") or 7 ("very much worse") for 2 visits in a row, the subject will be considered a non-responder and will receive the repeat [\frac{11}{C}]CUMI-101 and [\frac{11}{C}]DASB scans. They will then receive open treatment in our clinic.

IRB# 2012-1826-F PI: [name] Stony Brook University Human Subjects Committee (IRB) PSF 2/23/15

PSF 2/23/15 Page 21 of 37

Neither lithium nor lamotrigine is approved by the FDA for acute treatment of depressive episodes in patients with bipolar disorder, and neither drug is approved for treatment of unipolar depression. Thus, the use of both drugs as treatment for depression in this study is off-label. Nevertheless, both drugs represent reasonable treatment options for depression which has failed to respond to traditional antidepressants in either bipolar or unipolar depressive disorders. There have been several reports of the efficacy of lithium and lamotrigine in both bipolar and unipolar depression (175-178). In this study, unipolar depressed patients will only be treated with lithium.

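### A bipolar patient who has already failed lamotrigine 200 mg, but not lithium, can enter and then be directed back to lamotrigine at that same dose

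*Protocol*

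**What the plan says.** **Eligibility (Protocol D.4, bipolar Exclusion 12).** The criterion removes patients with "A documented history of a lack of response to a trial of adequate dose and duration of both lithium and lamotrigine". It defines a failed trial as minimal response to lamotrigine 200 mg for 4 weeks or more, or to lithium at a serum level of 0.8 or higher (or a dose of 900 mg or more) for 4 weeks or more.

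**Treatment (Protocol D.5, Treatment Choice).** Lithium is the first treatment. It is withheld after two or more failed trials at therapeutic levels. The next sentence gives lamotrigine to patients who did not respond to adequate earlier lithium or who refuse it. Two further rules lead from lithium to lamotrigine:

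- At 6 weeks, a patient short of a 50% gain falls under the rule ending "improvement in their HDRS score from the baseline interview they will be switched to lamotrigine".
- For intolerance: "if patients cannot tolerate treatment, they will be switched to lamotrigine".

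Lamotrigine starts at 25 mg bid, goes to 50 mg bid after 2 weeks and to 100 mg bid after 2 more.

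**Exits.** A patient leaves study treatment in three situations: "If subjects cannot tolerate either treatment"; a CGI severity score of 4 "or more after the week 4 visit for two visits in a row"; or a CGI improvement score of 6 or 7 "for 2 visits in a row, the subject will be considered a non-responder and will receive the repeat" scans. The section continues: "They will then receive open treatment in our clinic". A later sentence in the same section moves patients whose lithium or lamotrigine is not effective to open treatment, without saying when.

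**Scope.** "In this study, unipolar depressed patients will only be treated with lithium", so the point concerns bipolar patients only.

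**The concern.** Treatment Choice checks a patient's lithium history before giving lithium, but nowhere checks lamotrigine history before giving lamotrigine. All three routes to lamotrigine (refusal, week-6 non-response, intolerance) are written as directions, with no exception for a documented failure.

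The patient in question is a plausible entrant. Bipolar Inclusion 1 requires patients on psychiatric medication to have failed their current regimen. The drug-free-interval text in section G admits mood-stabilizer users only if they are non-responsive. Someone who arrives on lamotrigine therefore arrives as a non-responder to it, although the adequate dose in Inclusion 1 comes from a separate treatment form and need not be 200 mg.

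At stake is a second course of a drug already documented as ineffective for that person, in a depressed patient who has been through washout, and a later start of open treatment.

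**Working it through.** No sample size or power figure is in dispute. The check sets the rules side by side, with dose and time arithmetic.

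**1. Is the patient eligible?** The governing phrase in Exclusion 12 requires failure of *both* drugs. The definition that follows joins them with *or*. If *or* governed, one lithium failure would exclude, and the sentence in Treatment Choice giving lamotrigine to earlier lithium non-responders would have little purpose. *Both* is the better reading, so lamotrigine failure alone does not exclude.

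**2. Does the retrial repeat the failed dose?**

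| Weeks on lamotrigine | Dose | Daily total |
|---|---|---|
| 0–2 | 25 mg bid | 2 × 25 = 50 mg |
| 2–4 | 50 mg bid | 2 × 50 = 100 mg |
| from 4 | 100 mg bid | 2 × 100 = 200 mg |

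Target over Exclusion 12 threshold: 200 / 200 = 1.0, reading the criterion's 200 mg as a daily dose.

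**3. Where does a lithium non-responder stand at the switch?** Planned lithium on days 4–7 is 300 + 600 = 900 mg/day, then adjusted to a level of 0.8–1.2. Suppose week 6 counts from the first dose, and the dose is not later cut below 900 mg with the level under 0.8. Exposure is then day 4 to day 42: 42 − 4 = 38 days, and 38 / 7 = 5.4 weeks, more than the 4 in Exclusion 12. If response has been minimal, the patient then matches both halves of Exclusion 12 at the moment lamotrigine is directed.

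**4. How long could the retrial last?** Take therapeutic lamotrigine as 200 mg/day and the titration as written.

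- Switched from lithium, no early exit, rescan 4–10 weeks after the therapeutic dose: 4 + 4 = 8 to 4 + 10 = 14 weeks, of which 4–10 at 200 mg/day.
- Lithium refuser, no early exit, rescan 6–10 weeks after the therapeutic dose: 4 + 6 = 10 to 4 + 10 = 14 weeks, of which 6–10 at 200 mg/day.

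These are upper bounds. The CGI severity exit shortens them for patients rated 4 or more. With two-weekly visits, two visits after week 4 fall at weeks 6 and 8.

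- Switched at week 6, clock from study start: 8 − 6 = 2 weeks, all at 50 mg/day. If the week 4 visit counts, the exit falls at week 6 and there is no lamotrigine.
- Same patient, clock restarted at the switch: 8 weeks, of which 8 − 4 = 4 at 200 mg/day.
- Week 6 counted from the therapeutic lithium dose: if that is reached at week 2 (an illustration), the switch falls at 2 + 6 = 8, together with the exit, so there may be no lamotrigine.
- Lithium refuser: exit at week 8, with 8 − 4 = 4 weeks at 200 mg/day; if the week 4 visit counts, exit at week 6 with 6 − 4 = 2.

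The range is thus 0 to 14 weeks, and shorter still within each path if the open-treatment sentence is applied early.

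**5. How many patients?** Aim 4 expects 50% to be ineligible for lithium monotherapy, so about 38 × 0.5 = 19 bipolar patients start lithium. The share with earlier lamotrigine failure is not given, and the 19 is not the denominator for refusers. The number affected cannot be computed.

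**The case against.** **Retrial is partly a design choice.** The lithium rule withholds the drug only after two failed trials, so the protocol tolerates one earlier failure, although its next sentence is looser. Exclusion 12 also leaves every entrant at least one drug not documented as failed, and this patient is offered lithium first. This stands in part, and it lowers the severity. But lamotrigine has no history check at all, even after repeated failures, and Exclusion 12 treats one 200 mg trial as enough to count.

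**Existing exits and judgement may prevent the retrial.** The CGI rules, the open-treatment sentence and the psychiatrist's freedom to stop a drug for side effects (Clinical Monitoring) all help. Visits after week 4 also depend on clinical status, with only a monthly minimum. This stands as a limit on every duration above. It does not remove the gap: the severity exit misses patients rated below 4, the worsening exit needs a rating of much worse, the open-treatment sentence has no timing, and none of them refers to lamotrigine history.

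**A reader might infer a raised risk of serious rash.** Section G lists serious rash among lamotrigine's possible side effects. But this patient has by definition already taken 200 mg for at least 4 weeks, and nothing in the documents shows a higher risk than for any other lamotrigine patient.

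**A reader might extend the point to earlier lamotrigine intolerance.** That would rest on silence alone. The earlier dose may have been lower, and prescribing judgement or the exit for patients who tolerate neither drug may cover such cases.

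**Conclusion.** The point holds as a minor inconsistency between the entry and treatment rules. For a bipolar patient with documented lamotrigine failure and no lithium failure, following the written rules can repeat the 200 mg/day that the protocol already counts as failed. The cost to that patient is avoidable re-exposure to an ineffective drug and delay before open treatment, for between 0 and at most 14 weeks.

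This rests on *both* governing Exclusion 12, on 200 mg being a daily dose, on therapeutic lamotrigine meaning 200 mg/day, and on clinicians following the text. The durations also depend on when the week-6 clock starts and on visit timing, neither of which the protocol fixes.

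It might also be read as an eligibility breach, because a minimal lithium responder can match Exclusion 12 at the switch. It is not one: Exclusion 12 applies at entry, on documented history. Nor do the documents show any damage to the Aim 4 analysis.

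**What to change.** Add to the lamotrigine-assignment sentence and to both switch rules in Treatment Choice:

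- A bipolar patient with documented lamotrigine non-response, by Exclusion 12's definition, is not given or switched to lamotrigine.
- After lithium non-response at 6 weeks, that patient has the repeat scans and goes to open treatment by the section's existing non-responder route.
- If that patient refuses lithium, or stops it for intolerance before adequate exposure, the patient goes to open treatment without a required rescan. An early rescan could fall before the 6–10 week exposure window of Aims 2 and 3 and would add a PET session with an arterial line.

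The cost is a few lines in one section, using history already taken for Exclusion 12. The downside is somewhat fewer lamotrigine repeat scans for Aim 4; how many cannot be stated.
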